5. STUDY CONDUCT

5.1 Restrictions during the study

- Volunteers should be fasted overnight for 10 hours before investigational product administration (water is allowed up to 1 hour predose) and volunteers remain fasted for 4 hours after investigational product administration. Water is allowed 1 hour postdose.
- The volunteers will be fasted for at least 4 hours prior to any clinical laboratory evaluations. Postdose time points will be Days 7, 14, 28 and End of Study visit (not fasted).
- Volunteers with sexual partners who are pregnant or who could become pregnant (ie, women of child-bearing potential), are postmenopausal, surgically sterile, or using an effective hormonal method of contraception or intrauterine coil should use barrier methods of contraception for at least 6 months after [¹⁴C]-AZD9291 administration to avoid pregnancy and/or potential adverse effects on the developing embryo. Reliable methods of contraception should be used consistently and correctly. Two or more of the following methods are acceptable and must include at least one barrier method:

Acceptable methods for volunteers' partners include:

- Implants, injectables, combined oral contraceptives (which must all be combined with barrier methods of contraception), some intrauterine devices, vasectomised partner (which must all be combined with barrier methods of contraception), and sexual abstinence.

Acceptable methods for volunteers include:

- Volunteers will be required to use reliable methods of contraception (condom and spermicide) for the duration of the study until 6 months after the investigational product administration. If a man has had a vasectomy this should be considered an appropriate method of contraception (along with a condom).

Alternatively, true abstinence is acceptable when it is in line with the volunteer's preferred and usual lifestyle. If a volunteer is usually not sexually active but becomes active, they, with their partner, should use 2 of the contraceptive methods listed above.

- Volunteers must avoid fathering a child during the study and for 6 months after [¹⁴C]-AZD9291 administration.

- Volunteers should abstain from sperm donation for 6 months after [¹⁴C]-AZD9291 administration.
- Volunteers should abstain from donating blood during the study and for at least 3 months after the End of Study visit.
- Volunteers should abstain from taking drugs of abuse from 4 weeks prior to [¹⁴C]-AZD9291 administration and until 3 months afterwards.
- Volunteers should abstain from taking any prescribed medication, over-the-counter remedies, herbal medications, high-dose or ‘mega’ vitamins, mineral supplements, or medicines purchased via the Internet beginning 4 weeks (or longer depending on the medication’s half-life) before investigational product administration and continuing until 3 months after investigational product administration. Paracetamol 1 g, every 6 hours, to a maximum daily dose of 4 g is permitted; however, the Principal Investigator should be informed so this can be recorded.
- Volunteers should not consume grapefruit, grapefruit juice, Seville oranges, Seville orange marmalade, or other products containing grapefruit or Seville oranges from 7 days prior to [¹⁴C]-AZD9291 administration until after the End of Study visit.
- Volunteers who wear contact lenses should discontinue wearing their lenses if they have any mild to moderate eye symptoms following exposure to the investigational product for at least 1 week after symptoms have resolved.
- Volunteers should not use any eye drops or ointment for treatment of eye symptoms, unless agreed by a study doctor, at any time during the study up to 1 week after [¹⁴C]-AZD9291 administration.
- Volunteers should abstain from taking caffeine-containing drinks or foods (eg, coffee, tea, cocoa, chocolate, and cola) while in-patient during the study. During the outpatient period, volunteers should avoid excessive intake of caffeine-containing drinks or food, eg, coffee, tea, chocolate, caffeine-containing energy drinks (Red Bull), and cola (more than 5 cups of coffee or equivalent, per day). One caffeine unit is contained in the following items: 1 (6 oz) cup of coffee, 2 (12 oz) cans of cola, 1 (12 oz) cup of tea, ½ (4 oz) cup of energy drink (eg, Red Bull), or 3 oz of chocolate.
- Volunteers should abstain from drinking alcohol beginning 72 hours before admission to the study centre and continuing until 24 hours after leaving the study centre and also beginning 72 hours prior to blood tests or the End of Study visit.
- Volunteers should abstain from consuming poppy seeds from enrolment until after the End of Study visit.

- Volunteers should refrain from strenuous physical activity that is not within the volunteer's normal weekly routine, beginning 5 days before each visit to the study centre and continuing until after the End of Study visit.
- Volunteers should refrain from actively trying to lose weight from the prestudy physical examination until after the End of Study visit.

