c Blood sampling for genotyping is optional and will be collected if the volunteer provides additional informed consent on Day -1.

d Height/weight will be evaluated at the screening visit. Only weight will be evaluated on Day-1 and Day 84 (End of Study visit).

e A brief physical examination (including general appearance, skin, abdomen, cardiovascular system, and lungs) performed at admission or predose.

- f The volunteers will fast from overnight prior to clinical laboratory evaluations at screening. Postdose time points will be Days 7, 14, 28 and End of Study visit (not fasted).
- g Creatinine clearance will be estimated using the Cockcroft-Gault formula at screening.
- h Ophthalmic examination (best corrected visual acuity and slit-lamp fundoscopy and intraocular pressure measurement) will be conducted at screening (will be considered the baseline value; no need to repeat) and for cause (on occurrence of AE only).
- i A sample for urinalysis to be collected together with the other clinical laboratory evaluations. Microscopy will only be performed if abnormal urinalysis results are observed.
- j Alcohol will be assessed by an alcohol breath test. Smoking will be assessed by performing a breath carbon monoxide test. A positive test will constitute a value of greater than 10 ppm.
- k Supine blood pressure and pulse rate will be evaluated after the volunteer has rested in a supine position for at least 10 minutes. If possible, the same arm and equipment should be used for each evaluation (refer to [Table 3](#) for time points).
- l Refer to [Table 3](#) for ECG time points.
- m Volunteers will receive a single administration of the investigational product on Day 1.
- n Blood, plasma, urine and faeces samples will be collected (refer to [Table 3](#) for time points).
- o Discharge on Day 85.
- p Only SAEs will be collected from screening until the End of Study visit whereas AEs will be collected from Day -1 through to the End of Study Visit.

Table 3 **Schedule of assessments**

Time (Day/hours)	12-lead ECG	P & BP^a	Safety blood & urine^c	24-hour urine collection^b	Faecal collection^b	PK and Met-ID Blood/plasma	Food and Fluid Restrictions^c	Physical examination	Residency
Screening ^d	X	X	X					X	
Day -1 ^{d,e}							F ^f	X ⁱ	T
Predose	X ^g	X	X	T	T	X	D ^h	X ^j	
Dose (Day 1)							D		
0.5						X			
1	X	X				X	D ^h		
1.5						X			
2	X	X				X			
3						X			
4	X	X				X	F ^f , M		
6						X	F		
8	X	X				X			
10						X			
12	X	X				X			
18						X			

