Day 1 (24)	X ^g	X				X			
Day 2 (36)						X			
48						X			
Day 3 (72)						X			
Day 4 (96)						X			
Day 5 (120)						X			

Table 3 **Schedule of assessments**

Time (Day/hours)	12-lead ECG	P & BP^a	Safety blood & urine^c	24-hour urine collection^b	Faecal collection^b	PK and Met-ID Blood/plasma	Food and Fluid Restrictions^c	Physical examination	Residency
Day 6 (144)						X			
Day 7 (168)	X	X	X			X			
Day 8									
Day 9									
Day 10									
Day 11									
Day 12									
Day 13									
Day 14 (336)	X	X	X			X			
Day 15									
Day 16									
Day 17									
Day 18									
Day 19									
Day 20									
Day 21 (504)	X	X	X	⊥	⊥	X			⊥
Day 28 (672)			X	X	X	X			24 h
Day 29									
Day 35 (840)				X	X	X			24 h
Day 36									
Day 42 (1008)				X	X	X		X ⁱ	24 h
Day 43									

Table 3 Schedule of assessments

Time (Day/hours)	12-lead ECG	P & BP^a	Safety blood & urine^c	24-hour urine collection^b	Faecal collection^b	PK and Met-ID Blood/plasma	Food and Fluid Restrictions^c	Physical examination	Residency
End of Study visit (Day 84)			X			X			24 h
Discharge (Day 85)	X	X		X	X			X	

BP: blood pressure; D: drink; ECG: electrocardiogram; F: free access to food & fluid; M: meal; Met-ID: metabolite identification; P: pulse rate;
PK: pharmacokinetic

a Only supine BP is to be measured. BP will be recorded after the volunteer has been resting for 10 minutes.

b Urine and faeces will be collected using separate containers as specified in the Laboratory Manual.

c The volunteers will fast from overnight prior to clinical laboratory evaluations at screening. Postdose time points will be Days 7, 14, 28 and End of Study visit (not fasted).

d Drugs of abuse testing will be performed at screening and Day -1.

e A 10 mL blood sample will be taken prior to receiving the first dose of AZD9291 for pharmacogenetic analysis provided the subject has provided additional informed consent on Day -1.

f Meals to be consumed at the same times as planned in the 24 to 72 hours period after investigational product administration – as per the study centre standard procedures. Volunteers are to be provided with 240 mL of water 2 hours postdose. Volunteers will remain fasted until 4 hours postdose.

g Volunteers will have 3 12-lead ECG traces recorded at 10 minute intervals.

h Water is allowed up to 1 hour predose and again starting at 1 hour postdose.

i Physical examination on Day 42 will include weight.

j Brief physical examination conducted on Day -1 or predose.

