6. COLLECTION OF STUDY VARIABLES

The study assessments are described in the sections below. The study plan and timing of these assessments are detailed in [Table 2](#) and [Table 3](#). Additional assessments may be performed if the Principal Investigator considers them necessary for volunteer safety.

It is important that PK sampling occurs as close as possible to the scheduled time. In order to achieve this, other assessments scheduled at the same time may be initiated prior to the time point. The sequence at a particular time point is:

1. 12-lead ECG.
2. Vital signs (blood pressure and pulse rate).
3. PK blood sample.
4. Safety laboratory assessment blood sample.
5. PK urine sample.

Apart from the predose PK blood sampling, which should occur within 30 minutes prior to investigational product administration, other predose assessments may be performed up to 60 minutes prior to administration of the investigational product.

For occasions when more than one assessment is required at a particular time point, PK blood samples should be prioritised. Additional assessments may be performed if the Principal Investigator considers them necessary for volunteer safety.

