6.3.5 Laboratory safety assessment

Blood and urine samples for determination of clinical chemistry, haematology, and urinalysis will be collected at the time points indicated in the study plan (see [Table 2](#) and [Table 3](#)).

The laboratory variables to be measured are provided in Table 5.

Table 5 Laboratory safety variables

Haematology ^a	Clinical Chemistry ^a	Virology ^c	Urinalysis ^b	Drugs of Abuse
Basophils	Alanine aminotransferase (ALT)	Hepatitis B surface antigen	Bilirubin	Amphetamines
Eosinophils	Albumin	Hepatitis C antibody	Blood	Barbiturates
Haematocrit (packed cell volume- PCV)	Alkaline phosphatase Lactate dehydrogenase	Human immunodeficiency virus (HIV) antibody	Glucose	Benzodiazepines
Haemoglobin	Aspartate aminotransferase (AST)		Ketones	Cocaine

Haematology ^a	Clinical Chemistry ^a	Virology ^c	Urinalysis ^b	Drugs of Abuse
Lymphocytes	Bicarbonate		Leukocytes	Marijuana/cannabis.
Mean cell haemoglobin (MCH)	Bilirubin (total)		Nitrites	Methodone
Mean cell haemoglobin concentration (MCHC)	Bilirubin (direct) (only if total is elevated)		pH	Methamphetamine
Mean cell volume (MCV)	Calcium Chloride		Protein	Ecstasy
Monocytes	Lipase		Specific gravity	Morphine/opiates
Neutrophils	Creatinine		Urobilinogen	Phencyclidine
Platelet count	Gamma glutamyl transpeptidase (GGT)			Tricyclic antidepressants
Red blood cell (RBC) count	Glucose (fasting)			
White blood cell (WBC) count	Potassium Phosphate (inorganic) Protein (total) Amylase Sodium Urea			

- a Volunteers will fast from overnight prior to clinical laboratory evaluations at screening. Postdose time points will be Days 7, 14, 28 and End of Study visit (not fasted).
b Urinalysis to be performed by standard dipstick analysis. Microscopy should only be performed if the urinalysis shows a positive result.
c Only at screening.

At screening a blood sample will be collected to screen for hepatitis B surface antigen, hepatitis C antibodies, and HIV. Creatinine clearance will be calculated at screening using the Cockcroft-Gault formula:

$$\text{Estimated CrCL (mL/min)} = \frac{(140 - \text{age [years]}) \times (\text{body weight [kg]})}{\text{Serum creatinine (mg/dL)} \times 72}$$

Urine will be tested at screening and on Day -1 for drugs of abuse. Urine will be collected at the study centre. Alcohol will be assessed by an alcohol breath test. Smoking will be assessed by performing a breath carbon monoxide test. If a volunteer tests positive for drugs

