7. BIOLOGICAL SAMPLING PROCEDURES

7.1 Volume of blood

The total volume of blood that will be drawn from each volunteer in this study is as follows:

Table 6 Volume of blood to be drawn from each volunteer

Assessment		Sample volume (mL)	No. of samples	Total volume (mL)
Safety	Clinical chemistry	5	7	35
	Haematology	2	7	14
Pharmacokinetics		13	26	338 ^a
Pharmacogenetics (optional)		10	1	10
Total				397

a If an in-dwelling catheter is used, an additional 0.5 mL of blood will be collected to flush the catheter prior to collecting each sample.

The number of samples collected, as well as the volume required for each analysis, may be changed during the study (ie, if additional samples are drawn for repeated safety assessments). However, the maximum volume to be drawn from each volunteer during the study will not exceed 550 mL. To put this in context, a single withdrawal of 470 mL occurs during a regular blood donation.

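### Section 5.1 requires a 4-hour fast before every laboratory sample but labels the named postdose samples as not fasted, so the glucose change from baseline can set fed values against a fasted baseline

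*Protocol*

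**What the plan says.** The fasting instruction for safety laboratory samples appears in four places in the protocol, and the glucose label in a fifth.

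- **Section 5.1, general rule:** "The volunteers will be fasted for at least 4 hours prior to any clinical laboratory evaluations".
- **Section 5.1, next sentence of the same bullet:** "Postdose time points will be Days 7, 14, 28 and End of Study visit (not fasted".
- **Table 2 footnote f and Table 3 footnote c (Section 3.1):** "The volunteers will fast from overnight prior to clinical laboratory evaluations at screening". Both then repeat the sentence that labels the postdose visits non-fasted. Neither mentions a 4-hour fast.
- **Table 5 footnote a (Section 6.3.5), attached to the clinical chemistry and haematology columns:** the same content as those two footnotes.
- **Table 5, clinical chemistry column:** "Glucose (fasting".

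Three further sections govern how the values are used. Section 11.1.1 sets the laboratory baseline at Day -1 and falls back to the previous nonmissing evaluation. Section 12.2.3 summarises all continuous safety data as observed values and as change from baseline. Section 5.1 also fixes the fast before dosing: "Volunteers should be fasted overnight for 10 hours before investigational product administration".

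**The concern.** A site cannot satisfy both the general rule and the non-fasted label at the named visits, and nothing says which governs. Staff working from the table footnotes would take the postdose samples without any fast. Staff working from the first sentence of the 5.1 bullet would require 4 hours.

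Glucose is the analyte for which the protocol itself states a fasting condition. If fed postdose values are set against a fasted baseline, the summary can show a change that reflects meals. The study has one treated group and no comparator, so nothing in the table would separate a meal effect from a drug effect. Additional safety and tolerability information is a stated secondary objective (Section 2.2). The fasting state is fixed when the blood is drawn and cannot be restored at analysis.

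**Working it through.** The plan gives no figure to reproduce. The check sets the texts side by side and follows them to the planned summary.

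**Step 1. What can the postdose label mean?**

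| Reading of the non-fasted label | State of the named postdose samples | What remains wrong |
|---|---|---|
| Exception to the 4-hour rule | No fast required at Days 7, 14, 28 and End of Study (4 visits) | The general rule says any evaluation; the Table 5 glucose label is wrong at all 4 visits |
| No overnight fast, but 4 hours still apply | At least 4 hours | No text says this; the three table footnotes omit the 4 hours |
| Applies to End of Study only | Fed at 1 visit, at least 4 hours at the other 3 | Still contradicts the general rule and the Table 5 label at that visit |

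Each reading needs an edit.

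**Step 2. What is the fasting state of the baseline?**

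- *Predose sample.* Table 3 marks a safety sample predose. The pre-dosing fast is 10 hours, and Section 6 says "other predose assessments may be performed up to 60 minutes prior to administration of the investigational product". Fast at the draw = 10 h minus 0 to 1 h = 9 to 10 h.
- *Screening, as the fallback in Section 11.1.1.* Overnight fast, by the table footnotes.
- *Day -1 sample under the 5.1 rule.* At least 4 hours.
- *Day -1 sample without that rule.* Not fixed. The table footnotes state a fast only for screening, and the Day -1 row of Table 3 carries the code F, defined as "F: free access to food & fluid".

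Section 11.1.1 names Day -1 as baseline, Section 3.1 places clinical chemistry at the Day -1 admission, and Section 11.2 uses a Day -1 haematocrit. A Day -1 draw is therefore a serious possibility, and its fasting state is the least settled of the four.

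**Step 3. Combine the two.** Take the first reading in Step 1, which the three footnotes favour. Postdose glucose is then unfasted at 4 visits. In three of the four baseline cases the baseline is fasted, and the change from baseline mixes fasting states. In the fourth, the baseline may itself be fed. The mismatch may then vanish, but the fasting label in Table 5 is wrong before dosing as well as after.

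**Step 4. How far does it reach?** The mixed comparison affects one analyte's row in the change-from-baseline summary. Section 12.2.1 plans no hypothesis test. Recovery of radioactivity and the pharmacokinetic parameters do not use glucose, and individual values are still listed.

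**The case against.** The strongest defence is that the second sentence of the 5.1 bullet is an ordinary specific exception to a general rule, and that three footnotes agree with it. On that view only the glucose label is out of place. The agreement of the footnotes is real, and it makes the non-fasted reading the more likely one in practice. That reading, however, is the one that leads to the mixed comparison, and it leaves both the general rule and the Table 5 label incorrect.

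A second objection concerns the baseline. A reader might infer that it is certainly fasted, and hence that the mismatch is certain. The documents do not support that. The defined baseline is Day -1, and Section 5.1 is the only text that would require a fast for a sample taken that day. The comparison can be mixed; it need not be.

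A reader might also turn to Section 7.1, where Table 6 follows the words "The total volume of blood that will be drawn from each volunteer in this study is as follows" and counts 7 chemistry samples. It is tempting to match these to screening, predose and Days 7, 14, 21, 28 and 84, and to conclude that there is no Day -1 sample and so the baseline must be the fasted predose one. The count does not show this. Screening, Day -1, predose, Days 7, 14, 28 and End of Study also make 7. Table 6 proves neither a Day 21 draw nor the absence of a Day -1 draw. Whether Day 21 is sampled, and whether the baseline is drawn on Day -1 or predose, are separate scheduling questions.

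Third, little depends on this. The study has 8 volunteers and one 20 mg dose, abnormal values are flagged in listings, and Section 1.4.4 reports no clinically important biochemistry trends in patients. This stands and limits the severity.

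Finally, whether to summarise glucose change could be settled in the statistical analysis plan. That is fair for the summary, but the fasting state at the draw has to be settled in the protocol.

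**Conclusion.** Wrong as written; minor. The general rule in Section 5.1, the non-fasted label repeated in four places, and the glucose label in Table 5 cannot all be true for Days 7, 14, 28 and End of Study. If the non-fasted wording is followed, the glucose change from baseline is a fed-against-fasted comparison whenever the baseline is the predose sample, the screening fallback, or a Day -1 sample drawn under the 5.1 rule. Outside those cases the protocol does not fix the baseline's fasting state.

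No numerical size is given, because the documents contain no figure for a fed-fasted glucose difference. The consequence is limited to the glucose row of a descriptive safety table. It does not touch the primary mass balance endpoint or the pharmacokinetics. The conclusion assumes that sites act on the wording as printed and that glucose is included in the change-from-baseline summary, as the Section 12.2.3 wording on all continuous safety data implies.

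**What to change.** Choose one of two courses before the first sample is taken.

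1. State one fasting condition, for example at least 4 hours without food, for the baseline sample and every postdose chemistry sample. Put the same sentence in Section 5.1, Table 2 footnote f, Table 3 footnote c and Table 5 footnote a.
2. If postdose samples are to stay non-fasted, remove the 4-hour rule for them and the fasting label from glucose in Table 5, and do not summarise glucose change from a fasted baseline.

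The first course costs one sentence in 5.1 and three footnotes. Days 7 and 14 fall within residency at 168 h (7 × 24) and 336 h (14 × 24) after a morning dose, so a 4-hour fast means at most a later breakfast. Day 28 and the End of Study visit need one instruction to volunteers beforehand. The second course costs a few words and one summary row.

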5.2 Subject enrolment and initiation of investigational product

The Principal Investigator will:

1. Obtain signed informed consent from the potential volunteer before any study-specific procedures are performed.
2. Assign potential volunteer a unique enrolment number, beginning with 'E10001001'.
3. Determine volunteer eligibility. See Sections [4.1](#) and [4.2](#).
4. Volunteers will be assigned a unique subject number at the time of dosing in the format of 1001 to 1008

If a volunteer withdraws from participation in the study, then his enrolment code cannot be reused. Enrolment codes will be assigned strictly sequentially as volunteers become eligible for enrolment.

5.3 Procedures for handling subjects incorrectly enrolled or initiated on investigational product

Volunteers who fail to meet the inclusion/exclusion criteria should not, under any circumstances, be enrolled or receive investigational product. There can be no exceptions to this rule.

Where volunteers that do not meet the inclusion and/or exclusion criteria, are enrolled in error, or incorrectly started on treatment, or where volunteers subsequently fail to meet the study criteria post initiation, a discussion should occur between the AstraZeneca Clinical Pharmacology Alliance (CPA) Physician and the Principal Investigator regarding whether to continue or discontinue the volunteer from the study.

The AstraZeneca CPA Physician is to ensure all such decisions are appropriately documented. In situations where an agreement cannot be reached, the volunteer should be discontinued from the study.

